#### 12.1.4.2. Depression, Anxiety, Stress Scales (DASS)

The DASS (Crawford and Henry 2013) is a set of three self-report scales designed to measure the negative emotional states of depression, anxiety and stress. Each of the three DASS scales contains 14 items, divided into subscales of 2-5 items with similar content. The Depression scale assesses dysphoria, hopelessness, devaluation of life, self-deprecation, lack of interest/involvement, anhedonia, and inertia. The Anxiety scale assesses autonomic arousal, skeletal muscle effects, situational anxiety, and subjective experience of anxious affect. The Stress scale is sensitive to levels of chronic non-specific arousal. It assesses difficulty relaxing, nervous arousal, and being easily upset/agitated, irritable/over-reactive and impatient. Subjects are asked to use 4-point severity/frequency scales to rate the extent to which they have experienced each state over the past week. Scores for Depression, Anxiety and Stress are calculated by summing the scores for the relevant items.

The rating scale is as follows:

0 Did not apply to me at all

- 1 Applied to me to some degree, or some of the time
- 2 Applied to me to a considerable degree, or a good part of time
- 3 Applied to me very much, or most of the time

Scores of Depression, Anxiety and Stress are calculated by summing the scores for the relevant items.

The depression scale items are 3, 5, 10, 13, 16, 17, 21, 24, 26, 31, 34, 37, 38, 42.

The anxiety scale items are 2, 4, 7, 9, 15, 19, 20, 23, 25, 28, 30, 36, 40, 41.

The stress scale items are 1, 6, 8, 11, 12, 14, 18, 22, 27, 29, 32, 33, 35, 39.

The score for each of the subjects over each of the sub-scales, are then evaluated as per the severity-rating index below.

	Depression	Anxiety	Stress
Normal	0-9	0-7	0-14
Mild	10-13	8-9	15-18
Moderate	14-20	10-14	19-25
Severe	21-27	15-19	26-33
Extremely Severe	28+	20+	34+

A total DASS score will be derived as the sum of three scales. DASS (total and individual scale score) will be analyzed similarly as AE-QOL. The actual and change from baseline scores by domain and total will be summarized by visit and treatment. The DASS change from baseline will be analyzed using an ANCOVA mixed model. The estimated treatment difference for each BCX7353 dose– Placebo at each visit (ie, Baseline, and Day 29) will be displayed together with the 95% confidence interval and the associated p-value. Least Squares Means (LS Means) for each visit will also be presented with the standard error and the number of subjects contributing to the LS Means.

The number and percentage of subjects in the severity-rating index categories will also be summarized by treatment and visit. The responses to the individual DASS questions will also be listed.

The relationship among the AE-QOL, DASS domains and confirmed weekly HAE attack rate will be provided descriptively and graphically using Pearson or Spearman correlation coefficient statistics and scatter plots.

## 12.2. Extent of Exposure

The number of subjects exposed to study drug and the duration of treatment will be summarized by treatment group.

## 12.3. Treatment Compliance

Treatment compliance will be computed by determining the number of capsules taken relative to the number of capsules that should have been administered. Treatment compliance based on the

drug accountability page and dosing diary will be calculated separately using the same formula below.

For compliance (%) based on the dosing diary:

$$\text{compliance (\%)} = (\text{number of capsules taken}) / (\text{number of capsules expected}) * 100$$

For compliance (%) based on the drug accountability page:

$$\text{number of capsules taken} = \text{the number of capsules dispensed} - \text{the number of capsules returned}$$

$$\text{number of capsules expected} = (\text{date of the last dose} - \text{date of the first dose} + 1) * 3$$

Summary of treatment compliance will be presented by treatment group and method. The number and percentage for compliance expressed as a categorical variable (<80%, ≥80%) will be also presented by treatment group and method.

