### **5.3.3. Study BCX7353-203**

Interim efficacy, safety, PK, PD, and PK/PD results are available for Parts 1 and 2 of this ongoing proof-of-concept Phase 2 study in subjects with HAE. As of the cut-off date of 19 May 2017, 51 subjects with HAE were randomized and had received up to 28 days of treatment with BCX7353 once daily; 18 subjects received BCX7353 350 mg, 6 subjects received BCX7353 250 mg, and 7 subjects received BCX7353 125 mg. In addition, 20 subjects with HAE had received placebo. Part 3 of the study is currently ongoing.

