## 9. TREATMENT OF SUBJECTS

### 9.1. Description of Study Drug

BCX7353 is an oral small molecule inhibitor of plasma kallikrein. All subjects will receive 28 days of BCX7353 capsules or matching placebo for oral administration at one of the following doses:

- BCX7353 placebo QD orally (Parts 1, 2, 3 and 4)
- BCX7353 350 mg QD orally (Part 1)
- BCX7353 250 mg QD orally (Parts 2 and 3)
- BCX7353 175 mg QD orally (Part 4, if conducted)
- BCX7353 125 mg QD orally (Parts 2 and 3)
- BCX7353 62.5 mg QD orally (Part 3; Part 4 if conducted)

The study drug in this study consists of BCX7353 and placebo capsules. The active ingredient for this study is BCX7353, supplied by BioCryst. BCX7353 is a white to tan powder.

The BCX7353 capsules will be provided as hydroxypropyl methylcellulose (HPMC), size 00, opaque capsules. In Parts 1 and 2, capsules will be filled with drug substance to correspond to one-third of the total daily assigned treatment dose. Three capsules of BCX7353 will be administered orally QD for 28 days. In Parts 3 and 4, capsules will be filled with drug substance to correspond to one-half of the total daily assigned treatment dose. Two capsules of BCX7353 will be administered orally QD for 28 days.

The matching placebo will also be provided as HPMC, size 00, opaque capsules to match the BCX7353 capsules. The matching placebo will contain microcrystalline cellulose. Three capsules (Parts 1 and 2) or two capsules (Parts 3 and 4) of matching placebo will be administered orally QD for 28 days.

Additional details for the chemical and physical characteristics of BCX7353 may be found in the IB.

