### 9.2. Description of Study Drug Packaging, Labeling, and Storage.

Parts 1 and 2: The study drug will be packaged in bottles of 27 capsules per bottle and each kit will contain 2 bottles of study drug.

Parts 3 and 4: The study drug will be packaged in bottles of 32 capsules per bottle and each kit will contain 1 bottle of study drug.

Each kit will be labeled with the information required per local law and may include: Sponsor name, study protocol number, description of the contents, a statement regarding the investigational (clinical trial) use of the study drug, expiry date and kit treatment number.

Study drug will be stored between 15°C–25°C (room temperature).

Further details on the study drug will be provided in the study drug manual.

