#### **9.4. Study Drug (Investigational Medicinal Product) Administration and Treatment Compliance**

Subjects will take all study drug doses at home with the exception of study drug that will be administered under Investigator (or designee) supervision during scheduled on-treatment clinic visits on Days 1, 14 and 15 (and Day 28 if applicable). Subjects will be instructed to take 3 capsules (Parts 1 and 2) or 2 capsules (Parts 3 and 4) of study drug orally QD in the morning for 28 days. Subjects will be instructed to take study drug with food, or within 30 minutes after consuming food. On Days 1, 14 and 29, subjects should fast for 8 hours prior to their blood draw for laboratory testing.

The first dose of study drug will be administered in the clinic on Day 1. For study Days 14 and 15, subjects should be instructed to refrain from taking study drug prior to their visit to obtain a trough and/or serial blood draws at steady state.

On in-clinic dosing days (Days 1, 14 and 15), subjects will be required to consume food within 30 minutes prior to dosing (but after any blood draws for safety laboratory testing); the requirements for type and amount of food is to be provided to the subject (e.g., number of

servings of protein, carbohydrate, and/or fat) will be communicated in a separate document. On all other days, subjects should take the study drug in the morning with food (or within 30 minutes after consuming food). It is recommended that the study drug be administered with food in order to help minimize gastrointestinal effects. If gastrointestinal-related symptoms are noted as an AE, the site should query the subject and record whether the drug is being taken as instructed (i.e., with food).

Subjects will be instructed to maintain approximately the same daily dosing interval between study drug doses. If a subject forgets to take the study drug at the correct time, the dose may be taken later in the day; however, no more than 1 dose of BCX7353 should be taken on any calendar day. The subject should resume the standing regular dosing schedule on the next day.

Subjects will be instructed to record in their diary the time of day study drug was taken, and the number of capsules of study drug taken.

Subjects will be instructed to bring all drug kits (including both unused and used kit bottles) and diaries with them for each study visit. Accountability and adherence will be reviewed at each clinic visit.

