### 3. STUDY DESIGN

This is a Phase 2, randomized, double-blind, placebo-controlled, 3-part, parallel-group, dose-response study to evaluate the safety, tolerability, PK, PD, and efficacy of BCX7353 in subjects with HAE. HAE patients with a documented recent history of frequent angioedema attacks who have provided written informed consent will be evaluated for participation in this study at a screening visit. Up to 36 subjects with HAE are planned to be enrolled in Part 1 of the study and will be randomized 1:1 (placebo: active) to receive one of the following treatments:

- Part 1, Treatment Group 1: placebo QD orally for 28 days
- Part 1, Treatment Group 2: 350 mg BCX7353 QD orally for 28 days

After 24 subjects have completed through the Day 28 dose, there will be an administrative interim analysis of the accrued efficacy data by the Sponsor. Additional administrative analyses may be conducted following completion of Part 1 and Part 2.

If it is desired to more fully characterize the treatment effect of BCX7353 350 mg relative to placebo or to verify assumptions made for sizing this proof-of-concept study, additional subjects will be enrolled to complete Part 1 (up to 36). Enrollment into Part 1 will continue until either a decision is made to halt enrollment in favor of opening Part 2 or enrollment reaches 36 subjects in Part 1. Additionally, upon completion of Part 1 (36 subjects dosed), enrollment into Part 2 of the study may immediately commence.

In Part 2, approximately 14 subjects who meet all eligibility criteria are planned to be randomized in a 1:3:3 (placebo:active:active) ratio into 1 of the following 3 treatment groups:

- Part 2, Treatment Group 1: placebo QD orally for 28 days
- Part 2, Treatment Group 2: 125 mg BCX7353 QD orally for 28 days
- Part 2, Treatment Group 3: 250 mg BCX7353 QD orally for 28 days

If tolerability issues prevent full enrollment of Part 1 as described or study drug is poorly tolerated due to gastrointestinal effects, future subjects randomized to active study drug in Part 1 may receive 250 mg orally once daily for 28 days. In this case, any dose level changes warranted for Part 2 will be instituted via protocol amendment.

Following completion of enrolment in Part 2, Part 3 of the study may be initiated:

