**Table 4: Data Display Treatment Descriptors**

Study Part	Treatment Group	Treatment Description	Final Data Display
			Treatment Description
Parts 1, 2 and 3 Combined	Group 1	placebo QD orally for 28 days	Placebo
Part 1	Group 2	350 mg BCX7353 QD orally for 28 days	BCX 7353 350 mg
Part 2 and 3 Combined	Group 3	250 mg BCX7353 QD orally for 28 days	BCX7353 250 mg
	Group 4	125 mg BCX7353 QD orally for 28 days	BCX7353 125 mg
Part 3	Group 5	62.5 mg BCX7353 QD orally for 28 days	BCX7353 62.5 mg

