## **11.2. Protocol Deviations**

Subjects who were randomized but did not satisfy all inclusion and exclusion criteria will be listed. A listing of subjects for whom the treatment blind was broken during the study will also be provided, if appropriate. Subjects with dosing compliance <80% will be considered to have a major protocol deviation. Additional protocol deviations will be reviewed in a data review meeting to classify protocol deviations based on BioCryst Classification of protocol deviation Memo, and to discuss any statistical analysis issues.

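### The SAP compliance formula assumes 3 capsules a day for everyone, so a fully adherent Part 3 subject (2 a day) scores 66.7% and is recorded as a major protocol deviation

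*SAP*

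**What the plan says.** SAP 12.3 describes compliance as capsules taken relative to capsules that should have been given. It says that the accountability and diary versions are calculated separately but with the same formula. The only definition of the denominator is "number of capsules expected} = (\text{date of the last dose} - \text{date of the first dose} + 1) * 3", with no distinction by study part. Compliance is to be summarised by treatment group and method, both as a continuous value and split at 80%.

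SAP 11.2 attaches a consequence: "Subjects with dosing compliance <80% will be considered to have a major protocol deviation".

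On dosing, Protocol 9.4 states: "Subjects will be instructed to take 3 capsules (Parts 1 and 2) or 2 capsules (Parts 3 and 4". Protocol 9.1 says the same for Parts 3 and 4, "Two capsules of BCX7353 will be administered orally QD for 28 days", and gives the matching placebo count. Under Protocol 9.2, Part 3 drug is "packaged in bottles of 32 capsules per bottle and each kit will contain 1 bottle of study drug".

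Part 3 is within this SAP. Section 3 calls the study "randomized, double-blind, placebo-controlled, 3-part, parallel-group", and Table 4 displays the 250 mg and 125 mg arms under "Part 2 and 3 Combined".

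**The concern.** The factor of 3 fits Parts 1 and 2 but not Part 3. Applied as written, it understates the compliance of every Part 3 subject by a third and puts full adherence below the 80% line.

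Two outputs are directly affected: the compliance summary and the list of major protocol deviations. The error is also not evenly spread over the arms. The 62.5 mg arm comes only from Part 3, the 125 mg and 250 mg arms mix Parts 2 and 3, placebo mixes all three parts, and 350 mg comes only from Part 1. A dose-ranging report would therefore show adherence differing by dose purely because of the formula, with the lowest dose looking wholly non-compliant.

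A third output may be affected. The per-protocol (PP) population in SAP 6.4 requires at least 90% of planned drug by accountability and no significant protocol violations, and SAP 12.1.1 names PP beside the full analysis set (FAS) for the primary endpoint. If 6.4 were implemented through 12.3 or 11.2, adherent Part 3 subjects would drop out of PP.

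**Working it through.** The documents give no worked compliance percentage, so there is no stated figure to reproduce. The inputs are:

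- SAP multiplier: 3 per dosing day (SAP 12.3)
- Capsules per day: 3 in Parts 1–2, 2 in Part 3 (Protocol 9.1, 9.4)
- Dosing days: 28 (Protocol 9.1)
- Part 3 supply: 32 capsules per kit (Protocol 9.2), 2 kits per subject (Protocol 9.3.2), so 64 capsules
- Deviation threshold: below 80% (SAP 11.2)

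**1. Parts 1–2.** Taken 3 × 28 = 84; expected 28 × 3 = 84; compliance 100%. The formula is right here.

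**2. Capsule count in Part 3.** Each kit must cover 14 days plus overage. A 32-capsule kit lasts 32/2 = 16 days at 2 a day, but 32/3 = 10.7 days at 3 a day. The packaging agrees with 2 a day.

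**3. Fully adherent Part 3 subject.** Taken 2 × 28 = 56; expected 28 × 3 = 84; compliance 56/84 = 66.7%. For any number of days d the ratio is 2d/3d = 66.7%, so a subject who stops early having taken every dose gets the same score.

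**4. Ceiling by accountability.** If nothing is returned, the score is 64/(3d):

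| Days on drug | Ceiling |
|---|---|
| 28 | 64/84 = 76.2% |
| 27 | 64/81 = 79.0% |
| 26 | 64/78 = 82.1% |

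At 28 days, 80% needs 0.8 × 84 = 67.2 capsules, more than the 64 supplied. No Part 3 subject who completes 28 days on the two assigned kits can pass.

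**5. Effect by arm if everyone is perfectly adherent.** Parts 1–2 counts are those in Protocol 5.3.3 ("18 subjects received BCX7353 350 mg, 6 subjects received BCX7353 250 mg, and 7 subjects received BCX7353 125 mg", plus 20 on placebo). Part 3 is the planned 20 subjects at 1:3:3:3, that is 2 placebo and 6 per dose. Mean = (n in Parts 1–2 × 100 + n in Part 3 × 66.7) / total n.

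| Arm | Parts 1–2 | Part 3 | Mean compliance | Falsely below 80% |
|---|---|---|---|---|
| 62.5 mg | 0 | 6 | 66.7% | 6/6 |
| 125 mg | 7 | 6 | 84.6% | 6/13 (46%) |
| 250 mg | 6 | 6 | 83.3% | 6/12 (50%) |
| 350 mg | 18 | 0 | 100% | 0/18 |
| Placebo | 20 | 2 | 97.0% | 2/22 (9%) |
| All active | 31 | 18 | 87.8% | 18/49 (37%) |

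**6. PP, only if the 12.3 value or the 11.2 flag feeds 6.4.** PP would fall from 6 to 0 at 62.5 mg, 13 to 7 at 125 mg, 12 to 6 at 250 mg and 22 to 20 on placebo.

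**7. With a part-specific multiplier.** 56/(28 × 2) = 100%; the 80% line falls at 0.8 × 56 = 44.8 capsules.

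**The case against.** The strongest case on the other side does not dispute the arithmetic. It argues that the consequences are smaller and less certain than they look.

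- **General definition.** SAP 12.3 opens with a definition that is correct for every part, so the factor of 3 looks like text carried over from Parts 1–2. That is likely, but the explicit formula is what would be programmed, and it contradicts the definition.
- **Diary method.** The multiplier is printed under the accountability heading, and the shared formula could mean only the ratio. This stands in part: carrying it to the diary is the likelier reading, since no other denominator is given, but it is an inference. Section 16 lists a single compliance table, 14.3.1.1.2, based on accountability. That version is wrong on any reading.
- **Safeguards.** The data review meeting (SAP 11.2) or the revision clause (SAP 11.3) could catch the problem. This lowers the risk. Neither is written as an exception to the 80% rule, though, and the meeting is assigned the additional deviations rather than this one.
- **PP effect.** SAP 6.4 refers to the planned 28 days, does not cite 12.3, and uses a different term for violations. Deviations are classified under a sponsor memo that is not among the documents. This stands: the PP losses are hypothetical.
- **Arm counts.** They combine reported and planned numbers. This also stands: they are illustrations, whereas 66.7% and 76.2% follow directly from the documents.
- **Weight.** FAS is the population for efficacy, PP is additional, and Protocol 13.2.4 plans no formal hypotheses. That limits the severity but does not make the formula right.

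**Conclusion.** The concern holds: the formula is wrong as written for Part 3. A fully adherent subject there scores 66.7%, cannot exceed 76.2% by accountability over 28 days on the assigned kits, and is classed as a major protocol deviation. On planned numbers this touches about 20 of up to 70 subjects in Parts 1–3 (20/(36 + 14 + 20) = 28.6%), including the whole 62.5 mg arm.

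The by-arm figures assume perfect adherence, planned Part 3 enrolment and literal use of SAP 12.3 and 11.2. The PP effect further assumes a link to 6.4 that the SAP does not state. FAS, safety and PK/PD results are unaffected. It should be fixed because the compliance summary and the deviation list would otherwise be wrong, and wrong by different amounts at different doses.

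**What to change.** In SAP 12.3, replace the constant 3 with the capsules per day for the subject's part (3 in Parts 1–2, 2 in Part 3), and say that this applies to both the diary and accountability methods. If the SAP is later extended to Part 4, take that part's count from Protocol 9.1. This restates the protocol's existing capsule counts and changes nothing about dosing.

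Two short clarifications should go with it:

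- **SAP 11.2:** derive the 80% flag from the corrected value, and name which of the two methods drives it.
- **SAP 6.4:** compute the 90% criterion separately, as capsules taken by accountability over the planned 28-day total (84 in Parts 1–2, 56 in Part 3). Even when corrected, 12.3 cannot serve here because its denominator is actual days on drug. A Part 3 subject who stops on Day 10 with perfect dosing scores 20/20 = 100% by corrected 12.3, but has taken 20/56 = 36% of the planned supply. Also state whether an 11.2 major deviation counts as a significant violation for PP.

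The cost is one line in 12.3, a clarifying sentence each in 11.2 and 6.4, and two program derivations. No new data are needed.

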## **12.4. Adverse Events**

All AEs will be coded using the Medical Dictionary for Regulatory Activities (MedDRA 18.1). System organ class (SOC), high level group term, high level term, preferred term, and lower level term will be attached to the clinical database. A table showing the mappings of AE verbatim text to the coded terms will be provided.

Adverse events with an onset date and time prior to the first dose of study drug for the study will be assigned as a pre-dose AE for the listing and will not be included in the summaries.

Treatment-emergent AEs are defined as AEs that occurred on or after date of first dose of study drug and up to +30 days after the last dose. Investigators are not required to contact subjects after the last follow-up if it occurs prior to 30 days from last dose.

### **12.4.1. Adverse Event Severity and Toxicity Grading**

Adverse events are graded by the Investigator as Grade 1 (mild), Grade 2 (moderate), Grade 3 (severe), or Grade 4 (life-threatening) according to DMID Adult Toxicity Table (Draft, publish date : November 2007).

### **12.4.2. Summaries of Adverse Events**

Summaries of treatment emergent AEs will be provided for the Safety Population. No inferential statistics will be provided. A brief summary of AEs will show, by treatment group, the number and percentage of subjects who 1) had any AE, 2) had any drug-related event, 3) permanently discontinued from study drug due to an AE, 4) had any serious adverse event (SAE), 5) had any Grade 3 or higher AE, 6) had any Grade 3 or higher drug-related AE, 7) had any AE leading to interruption of study drug, 8), drug related SAE, or 9) died. Drug-related events are defined as those AEs in which the Investigator believes were possibly, probably, or definitely related to the study drug.

AEs will be summarized by treatment group. For each SOC and preferred term, the number and percentage of subjects reporting an event will be calculated. In summary tables, SOCs and events within a SOC will be presented by decreasing frequency count based on the total number

of events. Multiple events (by subject or SOC as appropriate) will be counted only once per subject per dose in each summary. For summaries that use severity grade, the most severe event will be selected.

The following summary tables (number and percentage of subjects) of treatment-emergent AEs (by SOC and preferred term) will be provided by treatment group:

- Overall summary of Treatment-Emergent adverse events
- Summary of treatment-emergent adverse events
- Summary of drug-related, treatment-emergent adverse events
- Summary of treatment-emergent adverse events by severity
- Summary of treatment-emergent Grade 3 or Grade 4 adverse events
- Summary of drug-related, treatment-emergent Grade 3 or Grade 4 adverse events
- Summary of serious treatment-emergent adverse events
- Summary of treatment-emergent adverse events leading to permanent discontinuation of study drug
- Summary of treatment-emergent adverse events leading to interruption of study drug
- Summary of drug-related, treatment-emergent serious adverse events
- Summary of Treatment-Emergent Rashes Considered Related to Study Drug

Data listings will be provided for all AE data. In addition to listing all AEs, distinct data listings will also be provided for 1) Grade 3 or Grade 4 AEs, 2) AEs leading to permanent study discontinuation, 3) SAEs and deaths, 4) Rashes.

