The Grade 3 event occurred in the 500-mg group and was a cutaneous rash with no mucosal involvement, no desquamation, or constitutional symptoms or laboratory abnormalities. This event was consistent with a Type IV hypersensitivity reaction, and resolved following treatment with oral and topical steroids. In the 500-mg group (Part 2), 1 subject experienced a Grade 2 headache, and 1 subject experienced Grade 2 upper abdominal pain upper and diarrhea (2 TEAEs) which led to the subject's discontinuation from study drug dosing. Additionally, Grade 2 syncope was experienced by 1 subject in the 250-mg group and Grade 2 upper abdominal pain in 1 subject in the 350-mg group. The Grade 2 upper abdominal pain led to the subject's discontinuation. In Part 3 following multiple dosing with 250 mg BCX7353, 1 subject experienced a Grade 2 maculo-papular rash. In Parts 1 and 2, the most commonly reported TEAEs were gastrointestinal disorders (eg, nausea and diarrhea) and nervous system disorders (eg, headaches). There was no apparent dose response with regards to any individual AE; however, more gastrointestinal adverse events (AEs) were reported in the higher dose cohorts. In Part 3, the most commonly reported TEAE was medical device site reaction (eg, skin irritation from the ECG electrode site). The next most frequently reported TEAE was a rash-like reaction in 3 subjects; however, only 1 was considered related to IMP. Across all parts of the study, there were no trends in laboratory abnormalities and the only Grade 3 or 4 laboratory abnormalities in BCX7353-treated subjects were 2 Grade 3 lipase values in the 350-mg group (Part 2) 3 days after discontinuing treatment that normalized or improved the following day. No significant increase of > 60 msec in QTcF was observed across dose groups and 1 subject in the 350 mg dose group (Part 2) had a single treatment emergent QTcF > 450 msec 3 days after discontinuing treatment (ie, 455 msec). Across all cohorts and treatments, no subject had a clinically significant ECG abnormality. With the exception of 1 subject with a >20% decrease in pulmonary diffusion testing ( $D_LCO$ ) result, no other clinically significant changes in  $D_LCO$  results were noted from baseline to end of dosing in the multiple day cohorts. In addition, no differences were seen comparing changes in  $D_LCO$  in BCX7353-treated with placebo-treated subjects.

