#### **12.1.1.3. Adverse Events of Special Interest**

For this protocol, nonserious treatment-emergent rashes will be considered events of special interest. This event in and of itself will not be considered serious unless it meets the criteria above. Events of rash regardless of severity or suspected relationship to study drug/IMP must be reported to the Sponsor Medical Monitor as described in Section 12.1.5.1. Management of rash possibly, probably or definitely suspected to be related to study drug/IMP, is provided in Section 12.2.1.

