#### **12.1.5.1. Reporting Events of Special Interest**

Although not an SAE, all events of treatment-emergent rash regardless of severity or suspected relationship to study drug/IMP must be reported by phone or email to the Sponsor Medical Monitor and in writing via email or fax using the SAE/Event of Special interest report form within 24 hours of the Investigator's assessment of the event. In addition, the event must be recorded on the AE CRF in real time. All additional follow-up evaluations of the event must be reported to BioCryst or its designee as soon as they are available. The SAE/Event of Special Interest report form should be sent to the following email addresses or fax numbers:

[name], Medical Monitor  
Cell number (24 hours) [contact]  
Email: [[contact]](mailto:[contact]); [[contact]](mailto:[contact])  
Safety [contact]

Immediate reporting should allow BioCryst to take the appropriate measures to address potential new risks in a clinical trial. Therefore, the initial report should be submitted by the Investigator within a very short period of time and under no circumstances should this period exceed 24 hours following awareness of the event. This also allows the independent DMC to review the emerging safety data in real time. In addition, the report form will allow a full clinical description and information regarding the evaluation that cannot be documented in the EDC due to free text limitations.

The follow-up report should contain information about the clinical course, medical evaluation, photographs, biopsy, and laboratory results.

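### The SAP's only rash-specific table is limited to rashes judged drug-related, so no planned output gives subjects with any treatment-emergent rash by arm

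*SAP*

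**What the plan says.** Protocol 12.1.1.3 sets the event: "For this protocol, nonserious treatment-emergent rashes will be considered events of special interest". It adds that "Events of rash regardless of severity or suspected relationship to study drug/IMP must be reported to the Sponsor Medical Monitor". Protocol 12.1.5.1 repeats the scope without the word nonserious: "all events of treatment-emergent rash regardless of severity or suspected relationship to study drug/IMP must be reported by phone or email". Neither section makes relationship to study drug a condition.

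SAP 12.4.2 lists the adverse event tables. The only one specific to rash is the "Summary of Treatment-Emergent Rashes Considered Related to Study Drug", numbered 14.3.1.11 in SAP 16. The same section defines the filter: "Drug-related events are defined as those AEs in which the Investigator believes were possibly, probably, or definitely related to the study drug".

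SAP 12.4.2 also plans a table of all treatment-emergent events regardless of cause (14.3.1.3) and a version by severity (14.3.1.5). The counting rule is: "For each SOC and preferred term, the number and percentage of subjects reporting an event will be calculated". A rash listing (16.2.7.5) is planned, with no stated limit on relationship.

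**The concern.** The protocol collects rash without a causality filter, and the one table devoted to rash applies one. A reader who wants the randomised comparison of the special-interest event, meaning the share of subjects with any rash on each dose and on placebo, finds no table that gives it.

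That count is useful because it does not depend on an opinion about cause. Protocol 5.4.4.2 says that all three presumed drug rashes seen so far appeared about 2 days after dosing ended, and the causality scale in Protocol 12.1.4 leans on temporal sequence. A rash with different timing could be called unrelated and drop out of the rash table. The same section wants the rash risk better defined and linked to HLA type, and both aims are easier with a fixed case definition.

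Without a term list set in advance, any pooled count made later depends on which terms someone then chooses. The protocol describes these rashes in several ways, including cutaneous rash, maculo-papular rash and maculopapular exanthema.

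**Working it through.** The plan states no figure to reproduce. The check is a comparison of outputs, followed by simple arithmetic for scale.

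**1. What each planned output gives for rash**

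| Output | Any cause? | One row per subject with any rash? | By arm? |
|---|---|---|---|
| Table 14.3.1.11 | No, related only | Not stated | Yes |
| Tables 14.3.1.3 and 14.3.1.5 | Yes | No, by SOC and preferred term | Yes |
| Listing 16.2.7.5 | Yes, no limit stated | No, a listing | Sorted by treatment (SAP 9.2) |

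No row answers yes in all three columns. Table 14.3.1.11 itself falls under this lead-in: "The following summary tables (number and percentage of subjects) of treatment-emergent AEs (by SOC and preferred term) will be provided by treatment group". So it is not certain that even the related rashes are pooled across terms.

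**2. Why the all-cause table does not yield the count**

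Let n_k be the number of subjects with rash term k in an arm, n_SOC the number in the SOC row, and R the number with any rash. If all the rash terms sit in one SOC:

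max(n_k) ≤ R ≤ min(Σ n_k, n_SOC)

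A subject with two rash terms counts in both rows, so Σ n_k can exceed R. The SOC row may include skin events that are not rash, so n_SOC can exceed R as well. As an assumed example, take an arm of 12 with two rash rows of one subject each. R is then 1 or 2, that is 1/12 = 8.3% or 2/12 = 16.7%, and the table cannot say which.

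**3. How much one subject matters**

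Protocol 5.3.3 gives 18 subjects on 350 mg, 6 on 250 mg, 7 on 125 mg and 20 on placebo. Part 3 plans about 20 subjects at 1:3:3:3, which is 20 × 3/10 = 6 per active dose and 20 × 1/10 = 2 on placebo.

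| Arm | Planned n | One subject |
|---|---|---|
| 350 mg | 18 | 1/18 = 5.6 points |
| 250 mg | 6 + 6 = 12 | 1/12 = 8.3 points |
| 125 mg | 7 + 6 = 13 | 1/13 = 7.7 points |
| 62.5 mg | 6 | 1/6 = 16.7 points |
| Placebo | 20 + 2 = 22 | 1/22 = 4.5 points |

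**4. An illustration of the filter**

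Protocol 5.3.1 reports, for Part 3 of Study BCX7353-101, "a rash-like reaction in 3 subjects; however, only 1 was considered related to IMP". A related-only table would show 1/3 = 33% of those subjects and leave out 2/3 = 67%. The section does not give their treatment assignments, so this shows the mechanism only.

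The 4.4% in Protocol 5.4.4.2 reproduces as 3/68 = 4.4%. It includes one Japanese subject, although Protocol 5.3.1 mentions three with rash-like reactions in that part. It counts a clinical picture in subjects dosed for at least 7 days, so the documents do not show that a relatedness rule removed the other two.

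**The case against.** The strongest reply is that nothing is lost. Table 14.3.1.3 shows every rash term by arm with no causality filter, Listing 16.2.7.5 covers rashes, and in arms this small a reader can count subjects by hand. This stands against the stronger reading that a reader might infer, namely that rash of any cause is never shown by arm. The documents do not support that reading. The reply does not supply the grouped count or a term list.

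A second reply is that there is no breach of the protocol. Protocol 12.1.1.3 and 12.1.5.1 are reporting rules and promise no table. Protocol 13.2.5 commits to summaries by preferred term, SOC and severity, and the SAP delivers them. Rash is not a listed safety endpoint in Protocol 7.2.3. The mandatory rash work-up, the discontinuation criterion and the DMC trigger all turn on suspected relationship, so a related-rash table fits how the protocol acts on rash. All of this stands, and it is a reason to keep the related row.

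A reader might also infer that the filter biases the comparison between arms. Investigators are blinded (Protocol 9.3.1), so timing and prior belief apply to active and placebo subjects alike. The filter can drop events, but the documents show no differential effect.

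**Conclusion.** The point holds as a gap in presentation. The rash-specific table is narrower than the event the protocol defines, and no planned output gives subjects with any treatment-emergent rash by arm. Severity is low, and the label is cheap improvement. No efficacy result, listed safety endpoint or stopping decision depends on it.

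For scale, one subject counted or not counted moves an active arm by 5.6 to 16.7 percentage points. This assumes that Part 3 enrols as planned and that Part 4, which the SAP does not cover, is left out. The 2 of 3 from Phase 1 should not be read as the size of an effect here: it comes from a different study in healthy subjects, with no arms given.

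**What to change.** - Retitle Table 14.3.1.11 *Summary of Treatment-Emergent Rashes* in SAP 12.4.2 and SAP 16.
- List the preferred terms that count as rash before unblinding for the final analysis. Interim data from Parts 1 and 2 have already been seen unblinded, so draw the list from the coding dictionary named in SAP 12.4 and not from the terms observed.
- Add a first row with the number and percentage of subjects with any treatment-emergent rash, regardless of relationship, for each dose, all active combined and placebo. Count each subject once. State in a footnote whether serious rashes are included, since Protocol 12.1.1.3 says nonserious and 12.1.5.1 covers all.
- Keep rashes considered related as a subset row.

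Counts and percentages are enough. SAP 12.4.2 rules out inferential statistics for adverse events, so confidence intervals are not needed.

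The cost is a short term list and one row block in an existing table. The all-active column is already the general format in SAP 9.1, and SAP 11.3 allows refinements of this kind.
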